This study utilized an unblinded design. Parents were approached prior to surgery. After informed consent was obtained, infants were randomized to 1 of 2 arms: either the morphine PNCA with a basal infusion (PNCA) group, or the morphine COI group. Randomization was stratified by gender and surgical location (thoracic, upper or lower abdomen) in blocks of 4. The randomization scheme was created by a statistician on the research team using Windows version 6.0 of “rand.exe” (<http://block-stratified-randomization.software.informer.com/>). The clinical research coordinator used the scheme to assign participants to groups.

Protocol Details

Morphine was administered using PNCA for Group 1 and COI for Group 2. Conditions were designed to replicate current pain management procedures in our NICU. For the PNCA group, orders were entered by a member of the Acute Pain Service (APS) or the patient's anesthesiologist. Using a 250 mcg/mL solution, PNCAs were ordered as morphine 0.010-0.0125 mg/kg button dose, 8 min lockout, 0.010-0.0125 mg/kg/hr basal rate, and 0.060 mg/kg/hour total maximum. Doses were rounded to the nearest microgram. Parents were instructed on signs of pain, to only push the PNCA button when the child was awake and in pain, never to push the PNCA button when the child was asleep, and to notify their nurse if they felt their child's pain was not well controlled. For the COI group, morphine was ordered at 0.030 mg/kg/hr with a 0.030 mg/kg/hr nurse bolus available each hour to a maximum of 0.060 mg/kg/hr total. Parents were instructed on signs of pain and to notify their nurse if their child's pain was not well

controlled. The post-surgical opioid delivery system was initiated upon return to the NICU. Based on our current practice, PNCA patients were managed by the APS and COI patients were managed by the neonatology team. COI patients were checked on daily by the APS, but opioid adjustments were made only by the neonatology team. Monitoring of all patients was consistent with current practice. Patients had continuous pulse oximetry and cardiopulmonary monitoring. Pain and sedation scores (Hoffman, Nowakowski, Troshynski, Berens, & Weisman, 2002) were recorded at least every 2 hours for the first 24 hours, with a minimum of every 4 hours thereafter. To calculate total opioid consumption, PNCA doses (PNCA group) and morphine boluses (COI group) were documented hourly.

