Enrolled patients who at any point prior to PNCA or COI discontinuation, subsequently required vasopressors, a high frequency oscillating ventilator, or benzodiazepines, acetaminophen or anti-inflammatory agents as adjuncts for pain were discontinued early from the study. At the time of the study, acetaminophen was not used as routinely as it is now. In order to not confound pain assessment and opioid consumption by having some patients receive it and others not, the study team chose to stop data collection if acetaminophen (or benzodiazepine) was administered. Data collection terminated for all other patients when the PNCA or COI was discontinued. However, patient orders were monitored for 5 additional days to assess whether methadone was started.

Independent variables were collected to describe the sample and to determine whether groups were equivalent on all potentially confounding variables. Demographic and anthropometric data were extracted from the electronic health record, and included gender, race, ethnicity, gestational age, weight at time of surgery, total time PNCA or COI was used, and whether the current surgery was the infant's first. We also recorded mechanical ventilation and

any unplanned re-intubation occurrences. PNCA injections and attempts, as well as COI boluses were recorded for day (0700-1859) and nighttime (1900 – 0659) shifts. Mothers were asked about perinatal use of antidepressant or illicit drugs.

Primary Outcome

Our primary outcome was opioid consumption, defined as the average amount of opioid consumed over the time on study, and reported in mg/kg/hr. For the PNCA group, it was calculated based on the number of hourly injections plus the basal rate. For the COI group, it was based on the infusion rate across the time on study and any boluses administered.

Secondary Outcomes

- 1) Average pain intensity over the time on study. Participant pain intensity was assessed using the Revised-Face, Legs, Activity, Cry, Consolability (Revised-FLACC) scale (Malviya, Voepel-Lewis, Burke, Merkel, & Tait, 2006), the scale currently used in our NICU for this patient population. The FLACC has been used previously for NICU infants (Ahn, Kang, & Shin, 2005), has been validated in numerous pediatric populations (McGrath et al., 2008), and was originally validated in children from 2 months – 7 years (Merkel, Voepel-Lewis, Shayevitz, & Malviya, 1997).

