Statistical analyses were calculated using SPSS 24 (IBM SPSS Inc., Chicago, IL) and SAS 9.4 software (SAS Institute Inc.). An unadjusted two-sided $P < .05$ was used for statistical

significance in all analyses. Unless otherwise noted, all analyses include data from post-operative days (POD) 0-3. All participants who received the allocated intervention, and had at least one post-randomized outcome were included in the modified intent-to-treat analyses. In addition, descriptive and frequency analyses were used to provide summary information about patient characteristics. We report the median (Mdn) with Interquartile range (IQR) throughout. A Wilcoxon signed rank test was used to compare paired data of day and nighttime injections and attempts for the PNCA group, and paired day and nighttime boluses for the COI group. A Mann Whitney test was used to compare PCNA and COI groups; comparisons based on categorical data were analyzed using Chi-square or Fischer's exact tests. We used a mixed model with random post-operative day (POD) to examine the associations between opioid consumption and considered covariates, which included race, gender, surgery location, gestational age, study group and POD. Covariance structure used was AR(1), model was estimated by using maximum likelihood, POD and intercept were modelled as random effects. To meet the normality assumption of the linear mixed model, the outcome opioid consumption was transformed by using logarithm at base 10. For model selection procedure, we first included one of the considered covariates in the model to examine any time-varying effects on the outcome (univariable model analysis), then repeated the same procedure for other covariates. Based on the univariable model analyses, any covariates and interaction terms with $P < 0.20$ were included in the final multivariable analysis. The final model only includes those covariates with $P < 0.05$. Adverse events are reported based on incidence collapsed across POD.

Sample Size/Power Analysis

Based on our retrospective study (Czarnecki et al., 2014), and using an estimate of a large effect size, we planned to include 30 patients in each group (60 patients total). This sample size

would have allowed for an 80% power at 5% significance level to use a t-test to detect opioid consumption differences between groups of at least 0.74 SD. The study was terminated early however, due to difficulty recruiting, time and cost constraints.

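### The mixed model for opioid consumption is fitted by maximum likelihood with no REML refit stated, so standard errors of between-infant terms are slightly too small: about 1.7% with one binary covariate and about 6% with all listed covariates (race taken as binary) at the planned N=60

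*Combined protocol and SAP*

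**What the plan says.** All of this is in the combined protocol and SAP.

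- **Estimation** (Statistical Analysis and Data Management): "Covariance structure used was AR(1), model was estimated by using maximum likelihood, POD and intercept were modelled as random effects". The outcome is opioid consumption on the log10 scale, for postoperative days (POD) 0 to 3. No REML fit and no small-sample degrees-of-freedom method is mentioned anywhere.
- **Candidate terms** (same section): "considered covariates, which included race, gender, surgery location, gestational age, study group and POD". The number of race categories is not given.
- **Entry and retention** (same section): each covariate is first modelled alone; then "any covariates and interaction terms with $P < 0.20$ were included in the final multivariable analysis"; then "The final model only includes those covariates with $P < 0.05".
- **Arm comparison** (same section): "A Mann Whitney test was used to compare PCNA and COI groups".
- **Levels of surgery location** (Design): "Randomization was stratified by gender and surgical location (thoracic, upper or lower abdomen) in blocks of 4", so location has three levels and uses two parameters.
- **Length of follow-up** (Protocol Details): infants withdrawn for certain treatments leave early, and "Data collection terminated for all other patients when the PNCA or COI was discontinued". The number of days can therefore differ between infants.
- **Size** (Sample Size/Power Analysis): 30 infants per arm were planned. The study stopped short of this, and the number analysed is not stated.

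**The concern.** ML estimates variance components as if the fixed effects were known. With a few dozen infants and several between-infant covariates, the between-infant variance is then estimated too low. The standard errors for study group, race, gender, surgery location and gestational age are too small as a result. The error always runs in the same direction.

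Opioid consumption is the primary outcome, and this is the only stated analysis that relates it to covariates. The model's own P values decide which terms remain. A between-infant term just above 0.05 under REML can therefore be kept as significant under ML, and any confidence interval reported from the fit would be too narrow.

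**Working it through.** **Planned N.** A two-sided 5% t-test with 30 per arm and a difference of 0.74 SD has 80.5% power by the noncentral t distribution, and the difference detectable at 80% power is 0.736 SD. The stated design reproduces, so N=60 is the planned size.

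**Parameter count r.** Intercept 1, study group 1, gender 1, surgery location 2, gestational age 1 (linear) and race 1 if binary (assumed) give r=7 for the full list. Race with three, four or five levels gives r=8, 9 or 10. One binary or continuous covariate alone gives r=2. Location alone gives r=3, and group plus location gives r=4.

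**Formulas.** For a between-infant term with equal follow-up, SE(ML)/SE(REML) = sqrt((N−r)/N). A nominal 5% test on the ML standard error rejects with probability P(|t| > t_crit × sqrt((N−r)/N)) on N−r df. That probability is also the largest REML P value that ML would report as below 0.05. The t reference on N−r df is an assumption, because the plan names no df method.

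**Two cases in full, N=60.**
- r=2: sqrt(58/60) = 0.9832, a shortfall of 1.68%. The cut-off is 2.002 × 0.9832 = 1.968, so the test rejects at 5.4%.
- r=7: sqrt(53/60) = 0.9399, a shortfall of 6.01%. The cut-off is 2.006 × 0.9399 = 1.885, so the test rejects at 6.5%.

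| N=60, terms in model | r | SE shortfall | Nominal 5% test rejects |
|---|---|---|---|
| One binary or continuous covariate | 2 | 1.7% | 5.4% |
| Surgery location alone | 3 | 2.5% | 5.6% (5.8% for the 2-df test) |
| Group plus location | 4 | 3.4% | 5.8% |
| All listed, race binary | 7 | 6.0% | 6.5% (7.0% for the 2-df location test) |
| All listed, race 3 levels | 8 | 6.9% | 6.7% |
| All listed, race 4 levels | 9 | 7.8% | 7.0% |
| All listed, race 5 levels | 10 | 8.7% | 7.3% |

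**Smaller N (assumed), r=2 to r=7.**

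| N | SE shortfall | Nominal 5% test rejects |
|---|---|---|
| 50 | 2.0–7.3% | 5.5–6.8% |
| 40 | 2.5–9.2% | 5.6–7.4% |
| 30 | 3.4–12.4% | 5.8–8.3% |

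**Entry screen.** At N=60 the P<0.20 univariable screen barely moves: 20.8% at r=2 and 21.2% at r=3.

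**Check of the formula by fitting.** ML and REML fits to simulated four-day data at N=60 gave shortfalls of 1.68% (r=2) and 6.01% (r=7), both with a random intercept plus AR(1) and with a random intercept plus random POD. With unequal follow-up (assumed 10/20/25/45% of infants with 1/2/3/4 days), r=7 gave 6.1–6.2% without POD interactions and 6.2–7.3% with them. Four-level race with interactions gave 8.1–9.0%. These runs used 25 data sets per scenario and assumed variances. AR(1) and random POD were not combined in one model.

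**Size of the effect on the test.** A larger simulation had 5,000 replicates, a random intercept and random POD, independent residuals, no group effect and assumed variances. ML and REML were fitted to the same data sets, both with N−r df. With four days per infant, ML rejected more often than REML by these amounts:
- N=60: 0.42 points (SE 0.09) at r=2 and 1.74 points (SE 0.18) at r=7.
- N=40: 0.58 points (SE 0.11) at r=2 and 2.12 points (SE 0.20) at r=7.

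Across scenarios, including unequal follow-up, REML with N−r df rejected at 5.2–6.1% and Kenward-Roger at 4.5–5.4%.

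**The case against.** The strongest reply is that the effect is too small to matter.

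- **Likely models are small.** Screening at 0.20 and retention at 0.05 make a seven-parameter final model unlikely. At r=2 to 4 and N=60, only a term with a REML P between 0.050 and about 0.054–0.058 would change status, and the documents show no such term. This stands and keeps the severity low.
- **Selection is the larger problem.** With five null covariates tested once each at 5% (assumed independent), the chance of at least one false retention is 1 − 0.95^5 = 22.6%. At 5.4% each it is 1 − 0.946^5 = 24.2%. This stands too. A reader might infer that a REML refit makes the final P values valid; it does not, because they remain post-selection.
- **The arms are compared by another method.** A reader might infer that the PNCA versus COI result on the primary outcome is compromised. The plan compares the arms by Mann-Whitney test, which uses no standard error from this model. Only the study-group term inside the mixed model is affected.
- **ML is legitimate for comparing fixed-effect structures.** It is, by likelihood ratio. The plan does not say that its P values come from such tests, and it states no REML refit for the final model.
- **Kenward-Roger goes beyond the defect.** Part of the excess left under REML is indeed not due to ML. Kenward-Roger deals with that small-sample remainder in the same refit.
- **No confidence interval from this model is mentioned.** This is correct, so the point about narrow intervals applies only if intervals are reported.

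**Conclusion.** The point holds, at low severity. The plan states ML, lets P<0.05 from that model decide retention and states no REML refit, so standard errors of between-infant terms are too small. At N=60 the shortfall runs from about 1.7% with one covariate to about 6% with all listed covariates and binary race. The lower end is more likely for the final model.

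A reader might take 6% as a ceiling. The documents do not support that. They give no number of race levels, and three to five levels give about 7–9%. They also admit interaction terms, and POD interactions with unequal follow-up can add to the shortfall. Nor is N=60 the analysed size: the trial stopped early, so the smaller-N figures above are assumptions that show the direction and range.

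The size is exact for equal follow-up and rests on a t reference with N−r df. The planned combination of AR(1) with random intercept and random POD was not itself simulated. Nothing in the documents shows that any particular term was wrongly kept.

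**What to change.** Use ML only for likelihood-ratio comparison of fixed-effect structures. Base the P<0.05 retention decisions on a REML fit with Kenward-Roger degrees of freedom. Take the final model's estimates, standard errors and P values, and confidence intervals if given, from the same fit. The plan describes the analyses as already done, so rerun the retention step this way, report that fit with the number of infants analysed and the number of race levels, and say whether any retained term changes.

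The cost is a change of estimation and df options in the mixed-model call, one rerun and one sentence in the SAP. The downside is wider standard errors and intervals. At N=60, REML adds 1/0.9832 − 1 = 1.7% at r=2 and 1/0.9399 − 1 = 6.4% at r=7. Kenward-Roger added about a further 2% to the standard error in simulation.

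### The mixed model's P-value rule has no exception for main effects, so study group or POD can be deleted while group-by-POD stays, and no arm contrast averaged over study days is specified

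*Combined protocol and SAP*

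**What the plan says.** The Primary Outcome section sets the target: opioid consumption, "defined as the average amount of opioid consumed over the time on study, and reported in mg/kg/hr".

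Statistical Analysis and Data Management gives two routes to an arm comparison. One is a Mann-Whitney test between the groups. The other is a linear mixed model on log10 consumption, fitted by maximum likelihood with AR(1) covariance and random intercept and POD, using POD 0-3. Its purpose is given as examining associations with candidate covariates: race, gender, surgery location, gestational age, study group and POD.

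Candidates are tried one at a time, with attention to time-varying effects. Then "any covariates and interaction terms with $P < 0.20$ were included in the final multivariable analysis", and finally "The final model only includes those covariates with $P < 0.05" (two-sided and unadjusted, like every other test in the plan).

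The plan does not force study group or POD into the model. It does not say that the main effects of a kept interaction stay, how POD is coded in the fixed part, or which arm contrast the model reports. It does not name either route as the primary analysis.

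**The concern.** The model can be left with a group-by-POD term but no group term, or no POD term. Such a model constrains the arms in a way nobody chose, and the constraint changes with the coding of POD. With a numeric POD starting at 0, removing group asserts that the arms consumed the same amount on POD 0. Removing POD asserts that the reference arm was flat over time, so the interaction then carries the other arm's trend instead of the difference in trends.

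An arm difference that changes over time is plausible here. Under Protocol Details the ordered background rate is 0.030 mg/kg/hr for COI and 0.010-0.0125 mg/kg/hr for PNCA, a ratio of 2.4 to 3 at the outset, and different teams manage the two arms afterwards. POD 0 is where those starting orders may weigh most, so an equality imposed on POD 0, or a coefficient that describes only POD 0, may represent the average over time on study poorly.

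At stake is the arm effect in the only analysis of the primary outcome that adjusts for covariates, including the stratification factors gender and surgical location.

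**Working it through.** **The plan's own figure.** Sample Size/Power Analysis gives 30 per group and 80% power for 0.74 SD by t-test. The noncentrality is 0.74 × √(30/2) = 2.87 on 58 degrees of freedom, and exact power is 80.5%. The figure reproduces. It concerns a t-test, so it does not cover a coefficient in a selected mixed model.

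**Algebra (numeric POD = 0, 1, 2, 3).** Let the arm difference in log10 consumption be D(POD) = b1 + b3 × POD.

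- All terms kept: the group coefficient is b1 = D(0). The equal-weight average over four days is b1 + 1.5 × b3, so b1 alone is off by 1.5 × b3.
- Group deleted, interaction kept: D(POD) = c × POD. An unweighted fit gives c = Σ(POD × D)/Σ(POD²) = (6 × b1 + 14 × b3)/14. The implied average is 1.5 × c = 0.643 × b1 + 1.5 × b3, since 1.5 × 6/14 = 0.643. The bias is -0.357 × b1.
- With a correlated covariance V, t = (0, 1, 2, 3)ᵀ and 1 a column of ones, the multiplier of b1 becomes 1.5 × (tᵀV⁻¹1)/(tᵀV⁻¹t). For the three assumed variance sets below it is 0.15, 0.07 and 0.37, so the bias is -0.85, -0.93 and -0.63 times b1. The -0.357 figure is therefore specific to the unweighted fit.

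**How often and how far (all assumed).** The documents give no SDs, so these log10 values are assumptions:

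- Set A: intercept SD 0.15, slope SD 0.05, residual SD 0.10, AR(1) 0.3.
- Set B: as A, with intercept SD 0.25.
- Set C: intercept SD 0.10, slope SD 0.05, residual SD 0.15, AR(1) 0.3.

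There were 20,000 simulated trials per scenario, 30 per arm, all four days observed, variances treated as known. The 0.05 rule was applied to the interaction and then to group. Ranges run over the three sets.

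| | b1 = -0.075, b3 = 0.05 | b1 = 0.08, b3 = 0.04 |
|---|---|---|
| True equal-weight average (ratio) | 0.000 (1.00) | 0.140 (1.38) |
| Interaction kept | 62-81% | 45-63% |
| Group then dropped | 49-79% | 64-82% |
| Reduced-model ratio in those trials | 1.17-1.20 | 1.20-1.28 |

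Part of the gap is selection. In the first scenario the full-model average in the same trials is 0.028 to 0.034, a ratio of 1.07 to 1.08; the rest comes from deleting group. Over all trials, without selection, the full-model contrast b1 + 1.5 × b3 averaged to the true value in every scenario.

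**Reading the coefficient alone.** Suppose the difference shrinks linearly from -0.15 on POD 0 to 0 on POD 3, so b3 = 0.05. The group coefficient back-transforms to 10^-0.15 = 0.71. The equal-weight average is -0.075, a ratio of 0.84. If days on study were uniform over 1-4 (assumed), the mean POD within an infant is 0, 0.5, 1 or 1.5, averaging 0.75. The per-infant target is then -0.15 + 0.75 × 0.05 = -0.1125, a ratio of 0.77. The gap from 0.71 is about half as large.

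**Other codings.** With centred POD the group coefficient is a mid-period contrast. With reference-coded categorical POD it is a reference-day contrast, and deleting group forces zero on that day. With full dummy (SAS-type) coding, the model without group has the same rank as the full model (8 of 8), so nothing is biased.

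**The case against.** A reader might infer that the mixed model misstates the average difference whenever group-by-POD survives. The documents do not support that. If group is kept, the model recovers the average by a linear combination, and nothing in the plan says the group coefficient would be reported as the average. Bias needs group deleted, its interaction kept, a coding where that costs a degree of freedom, and a non-zero difference on the constrained day. The coding is not stated, and SAS, one of the two packages named, allows a coding under which nothing is lost.

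A reader might also infer that the primary comparison is compromised. The Mann-Whitney test does not depend on this rule, and neither analysis is named primary.

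Nor do the documents record a decision to delete group. The retention sentence speaks of covariates and is silent on hierarchy, and they do not say whether a group-by-POD term was kept.

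The frequencies are also fragile. With intercept SD 0.18, residual SD 0.12, AR(1) 0.4, 60 infants and 1-4 days uniform (all but the 60 assumed), a drift of 0.15 log10 keeps the interaction in about 65% of trials with no random slope, 44-45% with slope SD 0.05 and 31-33% with 0.08. With 40 infants (assumed, because the trial stopped early) and slope SD 0.05 it is about 31%. In a simulation with these SDs and no random slope, a constant arm effect kept it in only 4-5%.

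All of this stands and limits the point. It does not remove the gap: a literal reading of the rule permits the deletion, and no average contrast is named.

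**Conclusion.** The point holds as a defect in the selection rule and an omission in reporting. Followed literally, the rule can leave group-by-POD in the model without study group or POD. If POD is numeric from 0, losing group forces a zero arm difference on POD 0 and biases the implied average, by -0.357 × b1 in the unweighted case and by more under the correlated structures tried. If group stays, the only hazard is reading its coefficient as the average.

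The algebra rests on the numeric 0-based coding, complete days 0-3 and equal day weights. The frequencies and ratios rest on assumed effects and variances and illustrate what could happen; they do not estimate what happened in this trial. The consequence is confined to the mixed-model arm effect.

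**What to change.** - Keep study group, POD and the main effects of any retained interaction in the mixed model, whatever their P values.
- State how POD is coded in the fixed and random parts.
- Report the arm contrast averaged over study days with its confidence interval, back-transformed to a ratio. State the day weights and match them as closely as possible to the Primary Outcome definition. Equal-weight least-squares means over POD 0-3 are not automatically that quantity, because infants with shorter courses contribute fewer days.
- Show group-by-POD as a separate, named secondary test with day-specific contrasts.

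Categorical POD is optional. Compared with a linear trend over four days it uses 2 more degrees of freedom for POD and 2 more for group-by-POD.

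The cost is SAP wording, a re-run on data already collected, and possibly slightly wider intervals from the extra retained terms.

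### Study group must reach P < 0.05 to stay in the opioid-consumption mixed model, so the adjusted treatment effect is missing when non-significant and too large on average when shown

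*Combined protocol and SAP*

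**What the plan says.** The Primary Outcome section makes average opioid consumption the primary outcome. Under Statistical Analysis and Data Management, a linear mixed model of log10 consumption is fitted with "considered covariates, which included race, gender, surgery location, gestational age, study group and POD". Selection has two stages. After one-at-a-time fits, "any covariates and interaction terms with $P < 0.20$ were included in the final multivariable analysis". Then "The final model only includes those covariates with $P < 0.05". Study group stands in the list on the same footing as race or gestational age, and no sentence keeps it in regardless of its P-value.

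The Design section says "Randomization was stratified by gender and surgical location (thoracic, upper or lower abdomen) in blocks of 4". Both of these factors are also on the candidate list.

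Outside the model, "A Mann Whitney test was used to compare PCNA and COI groups", and for summaries "We report the median (Mdn) with Interquartile range (IQR) throughout". Neither depends on a P-value. No test is named as the primary comparison, and no between-group difference with a confidence interval is specified.

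The Sample Size/Power Analysis section plans 30 per group, for 80% power with a t-test to "detect opioid consumption differences between groups of at least 0.74 SD". It adds: "The study was terminated early however, due to difficulty recruiting, time and cost constraints".

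**The concern.** Study group is the randomised contrast that the trial exists to estimate. A retention rule may be tolerable for nuisance covariates, but applied to the treatment term it does two things. If group is non-significant, the final model contains no treatment estimate, so a reader cannot see what range of differences the data allow. If group is significant, its estimate has passed a filter that removes the smaller values, so it overstates the effect on average. Both problems grow as the sample shrinks.

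The mixed model is also the only planned analysis that can adjust the comparison for the strata and use the daily data. Under the rule as written, a reader is left with an unadjusted P-value and two medians, or with an adjusted effect shown only because it was significant.

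**Working it through.** **Inputs from the document.** 30 per arm, two-sided 5% level, t-test, 0.74 SD (Sample Size/Power Analysis); P < 0.20 screen and P < 0.05 retention (Statistical Analysis and Data Management).

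**Assumptions.** True differences other than 0.74 SD; 20 or 15 per arm, because the achieved number is not given; the standardised difference is taken to apply on the scale of the model.

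**Step 1: the plan's own figure.** Noncentrality = 0.74 × √(30/2) = 2.87 with 58 degrees of freedom. Exact two-sided power is 80.5%, and the smallest difference detectable with 80% power is 0.736 SD. The stated 80% at 0.74 SD reproduces.

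**Step 2: the retention threshold.** In a two-group comparison, group is kept only if the observed difference, in observed SDs, exceeds t(0.975, 2n−2) × √(2/n).

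- n = 30: 2.002 × 0.258 = 0.517
- n = 20: 2.024 × 0.316 = 0.640
- n = 15: 2.048 × 0.365 = 0.748

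At 15 per arm, an observed difference exactly equal to the design effect of 0.74 SD would be dropped.

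**Step 3: what the filter does to the estimate.** A two-sample simulation (at least 100,000 trials per row) kept the estimate only if P < 0.05. In this setting any result with P < 0.05 has also passed the P < 0.20 screen, so the second filter is the one that binds.

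| True difference (SD) | Per arm | Group kept | Mean when kept (SD) | Ratio to truth |
|---|---|---|---|---|
| 0.30 | 30 | 20.8% | 0.647 | 2.16 |
| 0.50 | 30 | 47.5% | 0.712 | 1.42 |
| 0.74 | 30 | 80.5% | 0.828 | 1.12 |
| 1.0 | 30 | 96.8% | 1.019 | 1.02 |
| 1.5 | 30 | 100% | 1.500 | 1.00 |
| 0.74 | 20 | 62.4% | 0.926 | 1.25 |
| 0.74 | 15 | 49.9% | 1.021 | 1.38 |
| 1.0 | 15 | 75.2% | 1.148 | 1.15 |
| 1.5 | 15 | 97.8% | 1.519 | 1.01 |

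At 30 per arm, coverage of the 95% CI among kept estimates is 97% at 0.74 SD, 95% at 0.50 SD and 88% at 0.30 SD.

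**Step 4: the two-stage rule on daily data.** A second simulation used POD 0–3, random intercept and POD slope, AR(1) errors with an assumed correlation of 0.5, the P < 0.20 screen on five covariates (group, gender, location, race and gestational age), and backward removal at P < 0.05 (1,500 trials per setting).

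- 30 per arm: at 0.74 SD, kept 81.0%, ratio 1.12; at 0.50 SD, kept 47.3%, ratio 1.42; at 0.30 SD, kept 21.3%, ratio 2.22.
- 15 per arm: at 0.74 SD, kept 50.3%, ratio 1.42.
- Strata at 30 per arm, given assumed real effects of 0.3 SD: gender was dropped in about 80% of trials and location in 83–87%.
- With group, gender and location forced in, mean estimates lay within 0.012 SD of the truth, with 94–96% coverage.

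**Limits.** The covariance parameters were treated as known, and interaction terms were not screened. A patient-level linear model with the same two-stage selection gave closely similar results at 0.74 SD: kept 80% with ratio 1.11 at 30 per arm, and kept 51% with ratio 1.37 at 15 per arm.

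**The case against.** The strongest reply is that the group comparison does not rest on this model. The primary outcome is one average per infant, the groups are compared by Mann-Whitney, and the sample size assumes an unadjusted two-group test. The mixed model is introduced as a study of associations, so it may be read as secondary. This stands to the extent that the unadjusted comparison survives, and it limits the severity. However, the text does not call the model exploratory. It models the primary outcome with group as a term, and its coefficient will be read as the adjusted treatment effect.

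Other points have some force:

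- **The true effect may be large.** The starting orders in Protocol Details are 0.030 mg/kg/hr for the COI infusion against a PNCA basal rate of 0.010–0.0125. Matching the COI infusion alone would take (0.030 − 0.0125)/0.0125 = 1.4 to (0.030 − 0.010)/0.010 = 2.0 button doses per hour. At 1.0 SD or more with 30 per arm, inflation is 2% or less. This stands, but no SD is given, and the rule should not depend on the effect being large.
- **The bias at the design value is modest.** The excess is 0.828 − 0.74 = 0.09 SD, against a standard error of √(2/30) = 0.26 SD, or about a third of one standard error. This stands for 30 per arm. It does not answer the loss of the estimate in about 20% of such trials.
- **A univariable model containing group is fitted before any filter.** Nothing says that result is withheld, but it is not the adjusted estimate.
- **Dropping the strata costs little.** Under the assumed 0.3 SD effects (gender split evenly, locations in thirds), the added variance is 0.3² × 0.25 + 0.3² × (1/3) × (2/3) = 0.0425, or about 2% on the standard error. Because randomisation was stratified on them, omitting them from a linear model should not bias the group estimate. This stands, so the strata are the lesser part of the point.
- **A retained group-by-POD term might keep group in.** The plan does not say so, and that retention would itself depend on significance.

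**Conclusion.** The concern holds as a should-fix point. As written, the adjusted treatment estimate for the primary outcome is reported only on condition of significance. At the plan's design value with the planned sample, it would be absent in about 20% of trials and about 12% too large on average in the rest. With an assumed 15 per arm, it would be absent in about half and 38–42% too large in the rest. For assumed effects below the design value the overstatement is larger; for effects of 1.5 SD or more it is negligible. The wording of the rule is certain. Its effect in this trial is not, because neither the achieved sample size nor the true effect is in the document. The unadjusted comparison is intact, so the trial is not invalidated. The lack of a named primary comparison and of a between-group interval is a separate gap; it matters here because nothing else specified in the plan supplies the missing estimate.

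**What to change.** State that study group, gender, surgical location and, where daily data are used, POD are always in the mixed model and are exempt from both P-value rules. The rules may still be applied to race and gestational age. Report the group estimate with its 95% CI whatever its P-value.

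Name one analysis as the primary comparison and label the other group tests, including group-by-POD, as supportive. If the Mann-Whitney test is the one named, report a between-group difference with a 95% CI beside it.

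The cost is revised SAP wording and one re-run of the model, with no new data. The drawback is that a non-significant effect must then be shown with a wide interval.
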